#### PROCEDURES FOR ADMINISTERING SYNCHRONOUSLY PAIRED BRAIN AND HAND STIMULATION FOR SEVERE STROKE (total participant time: 1 hour each session):

1. Determining reaction time prior to the synchronously paired M1 stimulation with FES facilitated motor practice session: Prior to the practice session, we will determine each participant's reaction time required to release a spherical object (i.e. a lightweight ball of 10" diameter). We chose a large diameter spherical object because it allows maximum finger extension. The participants will first grasp the object when prompted by the 'Ready' visual cue and upon hearing an auditory 'Go' cue will extend the wrist and fingers to release the object within their ability. Participants will perform 20 trials. The spherical object is placed on a funnel shaped trough such that the participant's wrist and fingers can be placed directly on top of the spherical object. The spherical object is attached to the bottom of the trough with weighted strings, which will prevent the object from falling out of the trough. The Intan RHD2000 Recording Controller (IRC, Intan Technologies, Los Angeles, CA) will be used to record the EMG from the EDC muscle.

We will use the onset of EDC activity to determine reaction time. EMG will be rectified and smoothed (rsEMG) with a 10 Hz lowpass filter, and the onset time is defined as the point where the rsEMG increases to 10% peak amplitude.

2. Synchronously paired M1 stimulation with FES-facilitated motor practice session: Participants will be seated in a custom chair with their arms supported by height adjustable arm-rests. A host PC running MATLAB will display instructions and control the timing of events in each trial. An Arduino microcontroller (model Uno) is connected via USB to the PC and generates digital event markers and performs EMG onset detection in real-time. Each trial will begin with a 'Ready' cue, which prompts the participant to prepare and also initiate the start of data acquisition. An audible 'Go' cue (a 750 ms tone) is issued by the Arduino at a variable latency (5-8 s) after the 'Ready' cue. A timer set to the user-specific reaction time (see above) begins counting down at the onset of the 'Go' cue. When the reaction timer reaches zero, the Arduino issues a digital trigger to the TMS system, delivering a TMS pulse (at 70%, 100% or 130% intensity) to the "motor hotspot" either before FES (mean reaction time – 50-75 ms) or with the onset of FES (reaction time – 0 ms). TMS will be delivered with a MagStim 2002 Magnetic Stimulator, figure-eight 70 mm D coil (MagStim Ltd., Wales, UK) using the neuronavigation system (BrainSight, Rogue Research, Montréal, QC). The Arduino will also issue a digital trigger to the DS 7A stimulator (Digitimer, UK), which will deliver FES to the EDC muscle. DS 7A is a stimulator approved by the Food and Drug Administration, which can be used to provide functional electrical stimulation. Based upon previous studies (Cauraugh et al., 2009), we will provide FES according to six standardized settings: (1) 1 second ramp up; (2) 5 seconds of biphasic stimulation at 50 Hz; (3) 15 to 29 mA stimulation range; (4) pulse width of 200  $\mu$ s; (5) 1 second ramp down; and (6) 25 seconds of rest between trials. The trial ends and data acquisition stops 15 seconds after the "Go" cue. Participants will complete 200 trials of synchronously paired TMS and FES-facilitated motor practice within a session.

Synchronously paired M1 stimulation with FES-facilitated motor practice session duration: Each session will last approximately 1 hour. We will provide adequate rest breaks as needed. The participant can receive a maximum number of 20 sessions with an interval of at least one day between the consecutive session.

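### 200 trials with 25 s of rest between them cannot fit a session of about 1 hour: read literally the session takes about 150-160 min, and at least about 100 min on any reading that keeps the rest.

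*Combined protocol and SAP*

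**What the plan says.** All the timing is in the combined protocol and SAP, in the section on procedures for administering synchronously paired brain and hand stimulation, mostly in item 2.

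- Dose: "Participants will complete 200 trials of synchronously paired TMS and FES-facilitated motor practice within a session".
- Session length: "Each session will last approximately 1 hour". The section heading also gives 1 hour of total participant time per session, and item 1 under that heading adds 20 reaction-time trials.
- Start of a trial: "Each trial will begin with a" 'Ready' cue. The 'Go' cue "is issued by the Arduino at a variable latency (5-8 s") after it.
- End of a trial: "The trial ends and data acquisition stops 15 seconds after the" 'Go' cue.
- Rest: "6) 25 seconds of rest between trials". This is the last of six FES settings. The others include a 1 s ramp up, 5 s of stimulation and a 1 s ramp down.
- Number of sessions: "The participant can receive a maximum number of 20 sessions".

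The section on evaluation procedures for aim testing gives 3.5 h per session for same-day assessments, split into 2.5 h before and 1 h after the practice session.

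**The concern.** One hour shared among 200 trials is 18 s per trial. That is shorter than the 25 s rest and shorter than the 20-23 s trial, so each exceeds the hour separately.

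Staff therefore have to depart from at least one instruction. Keeping the trials and the rest means a session well beyond the stated participant time, on a day that already holds 3.5 h of testing for people with stroke. Keeping the hour and the rest means far fewer than 200 trials. The analysis section says the results are to inform larger studies, and a later study cannot reproduce a dose that this protocol does not fix.

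**Working it through.** **Inputs** (paired-stimulation procedures, item 2): 200 trials; 25 s rest; 'Ready' to 'Go' 5-8 s; trial end 15 s after 'Go'; FES 5 s plus two 1 s ramps. Extra breaks and the reaction-time trials have no stated length and are set to 0, so every total below is a minimum.

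**Formula:** session time = 200 × active time + 199 × 25 s.

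**The plan's own figure:** 3,600 s / 200 = 18 s per trial. No combination of the stated parts that keeps the rest gives this.

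**Each part alone**
- Rests: 199 × 25 = 4,975 s = 82.9 min.
- Trials with no rest: 200 × 20 = 4,000 s = 66.7 min, to 200 × 23 = 4,600 s = 76.7 min.

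**Literal reading** (rest from the end of one trial to the next 'Ready'; cycle 20 + 25 = 45 s to 23 + 25 = 48 s)
- 4,000 + 4,975 = 8,975 s = 149.6 min.
- 4,600 + 4,975 = 9,575 s = 159.6 min.
- Excess over 60 min: 89.6-99.6 min.

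**Sensitivity bound** (the 25 s is FES-off time, from the end of one FES train to the start of the next)
- Ramps inside the 5 s: 200 × 5 + 4,975 = 5,975 s = 99.6 min.
- Ramps added, 7 s train: 200 × 7 + 4,975 = 6,375 s = 106.3 min.
- Excess over 60 min: 39.6-46.3 min.

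Reaction time does not enter either reading. A middle reading, with rest from the end of FES to the next 'Ready', falls between them at 116-133 min if reaction time is taken as 0.

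**Length of the day with the 3.5 h of testing**
- As stated: 3.5 + 1 = 4.5 h.
- Literal: 3.5 + 2.49 = 5.99 h, to 3.5 + 2.66 = 6.16 h.
- FES-off: 3.5 + 1.66 = 5.16 h, to 3.5 + 1.77 = 5.27 h.

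**Trials that fit in 60 min with the rest kept** (no rest after the last): (3,600 + 25) / cycle, rounded down.

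| Reading | Cycle | Trials in 60 min | Cut from 200 |
|---|---|---|---|
| Literal | 45 s | 80 | 60% |
| Literal | 48 s | 75 | 62.5% |
| FES-off, ramps inside | 30 s | 120 | 40% |
| FES-off, ramps added | 32 s | 113 | 43.5% |

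**The case against.** **The hour is only approximate.** The smallest total is 99.6 min, 66% over. The 66.7 min for trials run back to back could pass for about an hour, but only by dropping the stated rest.

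**The time may be provided elsewhere.** It is not. The 3.5 h is fully used by testing (2.5 h + 1 h). The dose is set per session, so it is not spread over several. The allowance for further breaks, and the reaction-time trials, only add time.

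**A reader might infer that the trial-to-trial cycle is undefined.** The documents do not support that. Item 2 says where a trial starts and where it ends, so rest between trials literally runs from one to the other and gives 45-48 s. What remains is some ambiguity, because the rest is listed as an FES setting. The shorter totals are sensitivity bounds, not the plain text.

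**The consequences are limited.** This stands. The study is a single-group pre-post design with 10 participants that is meant to yield preliminary data, and the conflict is about operations and dose.

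**Conclusion.** The conflict holds. On the literal cycle the session is about 2.5 to 2.7 times the stated hour (149.6-159.6 min). On the most favourable reading that keeps the rest it is still about 100-106 min. These are minimum times, with breaks and reaction-time trials at zero.

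Three stronger conclusions might be drawn, and none is supported:

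- *That the hour is the mistaken figure.* Nothing shows which of the trial count, the rest and the session length is wrong.
- *That the results would be biased.* The paired t-tests, the sample size and the alpha do not depend on session length.
- *That every participant faces the excess 20 times.* Twenty is a maximum, and no planned number of sessions is given.

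The point should be corrected because it affects stated participant time and a reproducible dose.

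**What to change.** The sponsor should confirm which figure governs and bring the others into line.

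- **If 200 trials and 25 s of rest stand:** restate the session length in item 2 and the participant time in the section heading as about 2.5-2.7 h on the literal cycle, or about 1.7-1.8 h if the 25 s is FES-off time, plus breaks and the reaction-time trials.
- **If the hour and the 25 s of rest stand:** restate the dose as about 75-80 trials on the literal cycle, or 113-120 if FES-off time. This cuts the dose by roughly 40-63% and is a design choice for the sponsor, not an edit of wording.
- **If 200 trials and the hour stand:** the rest must be shortened, and so must the trial window, because 20-23 s already exceeds the 18 s available.

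In each case, state from what point the rest runs, and report the number of paired trials delivered per session. Item 2 says the controller "generates digital event markers" and that acquisition starts and stops with each trial, so the recordings should allow a count without a new log.

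The first option costs a less favourable stated participant time, more laboratory time if only an hour was booked, and possible fatigue before the same-day post-testing.

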## STATISTICAL ANALYSIS

Preliminary Analyses: Thorough exploratory data analyses will be conducted to ascertain data characteristics and to screen for outliers. The preliminary exploration of the data will be used to: 1) examine univariate and bivariate distributions; 2) investigate the magnitude of the associations between the dependent variables and the potential covariates (age, gender, time since stroke, stroke severity, upper extremity severity and

affected side); and 3) verify assumptions of the planned primary analyses. Although statistical results will be examined and interpreted, meaningful changes will be recorded as preliminary data to inform larger, more confirmatory projects. We will use an intent to treat approach, whereby all individuals will be retained for analyses, regardless of missing data. Missing data will be examined using available data on subject characteristics. Statistical significance will be set to .05 unless otherwise specified.

**Sample size:** We will recruit 10 participants to achieve 80% power using a paired *t*-test with an alpha of .05.

**Primary Analyses:**

**Aim: To determine the effect of synchronized stimulation on motor performance and use-dependent plasticity after stroke**

We will conduct three separate paired *t*-tests to examine changes in use-dependent plasticity and motor performance before and after the synchronized stimulation intervention. For use-dependent plasticity, we will evaluate percent change in peak-peak amplitude of the motor evoked potentials and for motor performance we will evaluate percent change in the finger extensor muscle force and number of blocks in the Box and Block Test. Data will be analyzed with an alpha of .05.
